15.4. Data Analysis

All statistical inference analyses will be performed with 2-sided tests at a significance level of 0.05, and 2-sided 95% confidence intervals (CI) will be calculated whenever appropriate. All data will be summarized by treatment group and visit as appropriate. All subject data will be presented in data listings by subject.

15.4.1. Efficacy Analyses

15.4.1.1. Assessments from Binge Eating Diary

The number of binge days per week at each assessment timepoint will be derived based on clinician review of the binge eating diary collected in the time intervals as follows:

- Baseline: binge eating diary completed for 14 consecutive days immediately prior to the Baseline visit and starting no sooner than the day after the screening visit;

- Weeks 1, 2, 3, and 4 (ie, Visits 3, 4, 5, and 6): binge eating diary collected at each visit, which will span from the previous visit to the current visit and therefore cover Weeks 1, 2, 3, and 4, respectively;
- Weeks 6, 8, 10 and 12 (ie, Visits 7, 8, 9, and 10): binge eating diary collected at each visit, which will span from the previous visit to the current visit and therefore cover Weeks 5/6, 7/8, 9/10, and 11/12, respectively.

Specifically, the number of binge eating days per week at baseline is calculated as the number of binge eating days in the 14 days immediately prior to the Baseline visit multiplied by 7 and divided by the number of days in the Baseline period (ie, 14 days); the number of binge days per week in a visit that spans between 2 scheduled visits is calculated as (total number of binge days) x 7 / (total number of assessed days in the visit span). If missing diary entries exist during an assessed period for a subject, the available non-missing diaries from the subject will be used to derive the number of binge days per week adjusted by the number of non-missing diary days accordingly.

15.4.1.2. Primary Efficacy Endpoint Analyses

The primary efficacy endpoint is the change from baseline in the number of binge days per week at Week 12.

15.4.1.2.1. Primary Efficacy Analyses

The primary efficacy analyses of the primary efficacy endpoint (the change from baseline in the number of binge days per week at Week 12) will be performed using a likelihood-based mixed model for repeated measures (MMRM). The response (dependent) variable is the change from baseline in the number of binge days per week assessed at Weeks 1, 2, 3, 4, 6, 8, 10, and 12. Specifically, the MMRM model includes fixed effects terms for treatment, visit (as a categorical variable), pooled center, baseline binge days category (stratification factor; refer to [Section 7.2.1](#) for categories), the number of binge days per week at baseline, and treatment-by-visit interaction. Restricted maximum likelihood estimation method will be applied using an unstructured covariance model. The Kenward Roger approximation will be used to estimate denominator degrees of freedom. In case of a failure of convergence with the unstructured covariance, the following structures may be assessed in a sequential order: heterogeneous Toeplitz, Toeplitz, and spatial exponential covariance pattern model. Of the above 3 covariance structures, the first covariance structure yielding convergence in the MMRM model will be used for the MMRM analysis. The spatial exponential model is selected for the analysis of data with unequally spaced time points. The LS mean treatment differences (each dasotraline group minus placebo group) of change from baseline at Week 12, their 2-sided 95% CIs, and the associated p-values will be calculated based on this model.

The normality assumption underlying the primary MMRM model will be assessed graphically. Conditional studentized and scaled residuals will be plotted against the predicted values, respectively, and Q-Q (quantile-quantile) plots of these residuals versus the expected quantiles of the standard normal distribution will be presented to provide a graphical view of similarity and difference in the two distributions. Cumulative distribution function (CDF) of the primary endpoint will be also provided by treatment group.

The primary efficacy analysis will be repeated for the PP population to examine the impact of premature dropouts and/or protocol deviations.

15.4.1.2.2. Supportive Analyses

The primary efficacy endpoint also will be analyzed using an analysis of covariance (ANCOVA) model and the last observation carried forward (LOCF) approach, as a supportive analysis. The model will include terms for treatment, pooled center, baseline binge days category (stratification factor), and the number of binge days per week at baseline as covariates.

15.4.1.2.3. Sensitivity Analyses

To address early dropouts under the assumption of missing not at random (MNAR), a pattern-mixture model using a placebo-based multiple imputation method and a pattern mixture model using multiple imputations with penalties (ie, deflating the individually estimated treatment effect size by known factors) will be performed as sensitivity analyses to explore the robustness of the MMRM results for the primary analysis. In case of a deviation from the assumptions required for the primary analysis, to confirm the robustness of the primary analysis result, 2 additional sensitivity analyses will be performed: (1) permutation test: fit a large number of datasets based on a same MMRM for the primary analysis with randomly assigning pseudo-treatment group designations; (2) generalized linear mixed model (GLMM) analysis: fit count data over time (ie, number of binge days among number of assessed days at each period) based on a binomial distribution. The details of these sensitivity analyses will be outlined in the SAP.

15.4.1.3. Key Secondary Efficacy Endpoints Analyses

The key secondary efficacy endpoints involved in the hypothesis testing of each dasotraline dose (4 mg/day and 6 mg/day) versus placebo include change from baseline at Week 12 in BE-CGI-S score and Y-BOCS-BE total score, and percent of subjects with a 4-week cessation from binge eating. If a subject is early terminated in the double-blind treatment period prior to collection of 28 days of diary data or the subject has missing diary data in the last 28 days prior to Week 12/EOT the subject will be counted as having no cessation.

Continuous key secondary variables (ie, change in BE-CGI-S score and Y-BOCS-BE total score) will be analyzed with an MMRM model similar to the primary efficacy analysis ([Section 15.4.1.2.1](#)) adjusted with the corresponding baseline. The LS mean treatment differences (each dasotraline group minus placebo) of change from baseline at Week 12, their 2-sided 95% CIs, and the associated p-values will be calculated based on the model.

Categorical secondary efficacy endpoints (ie, percent of subjects with a 4-week cessation from binge eating) will be analyzed using a logistic regression model with treatment, baseline binge days category (stratification factor; refer to [Section 7.2.1](#) for categories), and baseline number of binge days per week as covariate using a LOCF approach based on the ITT population. The odds ratios, their 2-sided 95% CIs, and the associated p-values for each dasotraline group over the placebo group will be derived from the model.

Additional supportive and sensitivity analyses may be conducted as needed for the key secondary endpoints to address early dropouts or potential deviation from the model assumption(s). To address early dropouts or potential deviation from the model assumption(s), supportive and sensitivity analyses similar to those described in [Section 15.4.1.2.3](#) may be

conducted as needed for the continuous key secondary endpoints. For the categorical key secondary endpoint, supportive and sensitivity analyses, such as a GLMM analysis with random effect(s) and a pattern-mixture model using placebo-based multiple imputations, may be conducted as appropriate. The details will be provided in the SAP.

15.4.1.4. Multiplicity Adjustment

To control the overall type I error rate strongly at 5% for the primary and key secondary endpoints, for the hypotheses to be tested (see [Section 15.2](#)), a sequential testing strategy will be used. Following the fixed sequence closed testing procedure in [Figure 2](#), testing will only proceed conditional on the statistical significance of the test(s) of prior level(s) at a 2-sided 5% significance level. See [Section 15.2](#) for details about the definition of statistical hypotheses.

Figure 2: Fixed Sequence of Hypothesis Testing for Primary and Key Secondary Efficacy Endpoints

[figure not shown]
[figure not shown]

Figure 2: Fixed Sequence of Hypothesis Testing for Primary and Key Secondary Efficacy Endpoints (Continued)

15.4.1.5. Other Secondary Efficacy Endpoints Analyses

The other secondary endpoints are:

- Change from baseline in number of binge days per week at Weeks 1, 2, 3, 4, 6, 8, and 10
- Change from baseline in number of binge episodes per week at Weeks 1, 2, 3, 4, 6, 8, 10, and 12
- Change from baseline in BE-CGI-S score at Weeks 2, 4, 6, 8, and 10
- Change from baseline in Y-BOCS-BE total score at Weeks 2, 4, 6, 8, and 10 and subscale scores (obsessions and compulsions) at Weeks 2, 4, 6, 8, 10, and 12
- Change from baseline in MADRS total score at Week 12
- Change from baseline in HAM-A total score at Week 12
- Change from baseline in SDS total score and subscale scores (school/work disability, social life disability, and family life disability) at Weeks 6 and 12
- Proportion of binge eating responders (ie, $\geq 75\%$ reduction in the number of binge eating episodes) at Week 12
- Change from baseline in EDE-Q modified including EDE-Q7 global score and 3 subscale scores (dietary restraint, shape/weight overvaluation, and body dissatisfaction) at Week 12

Continuous variables (ie, change in number of binge days per week, number of binge episodes per week, BE-CGI-S, Y-BOCS-BE total score, and SDS total score and subscale scores) will be analyzed using an MMRM model similar to the primary efficacy analysis ([Section 15.4.1.2.1](#)) adjusting for the corresponding baseline. Other continuous variables (eg, change in EDE-Q7 global score and subscale scores) will be analyzed using an ANCOVA model similar to the supportive analysis for the primary efficacy endpoint ([Section 15.4.1.2.2](#)), adjusting for the corresponding baseline as a covariate.

The proportion of binge eating responders at Week 12 will be analyzed using a logistic regression model and LOCF approach with factors of treatment, pooled center, baseline binge days category (stratification factor), and baseline number of binge episodes per week as covariate. For subjects who are discontinued, binge eating responders at Week 12 LOCF is defined per the last post-baseline time period during the treatment period that binge diary is assessed. To ensure that the logistic regression model is feasible, pooled center may be removed from the analysis model if some pooled center has no responder either because of a small number of subjects in the pooled center or subjects experiencing little change. As a supportive analysis, the proportion of binge eating responders over time will be analyzed by an inverse probability weighting (IPW) Generalized Estimating Equations (GEE) model. The details will be provided in the SAP.

In addition, the number and percentage of subjects in the following categories for reduction in the number of binge eating episodes from baseline will be summarized over time by treatment:

- cessation (defined as 100% reduction)
- 99% to 75% reduction
- 74% to 50% reduction
- other

15.4.1.6. Subgroup Analyses

The primary efficacy variable (the change from baseline in the number of binge days per week at Week 12) and a key secondary variable (ie, change from baseline in BE-CGI-S at Week 12) will be examined to explore the consistency of the treatment effect across certain subgroups at Week 12. Subgroups, including but not limited to gender, race and age group, will be detailed in the SAP. For each subgroup, subgroup analysis will be conducted based on a similar MMRM model to the corresponding primary efficacy analysis with 3 additional terms: subgroup, treatment-by-subgroup interaction, and 3-way interaction of treatment*subgroup*visit. Summary statistics with 95% CIs will be provided by treatment group within each subgroup, as well.

15.4.2. Safety Analyses

Safety data including AEs, laboratory values, ECG, vital signs, weight, C-SSRS, and other assessments will be analyzed by treatment group based on the DB Safety population (for data up to the end of treatment period) and Withdrawal safety population (for data collected during the withdrawal period), separately, as appropriate.

The data (including CSSA, DESS, MADRS, and HAM-A), which are used to assess physical dependence and withdrawal symptoms, will be analyzed by treatment for data collected in the withdrawal period based on the Withdrawal safety population.

Unless otherwise specified, for continuous data collected in the withdrawal period, the actual value and change from Week 12/EOT (last value during the treatment period) will be summarized by treatment and visit.

15.4.2.1. Adverse Events

All AEs will be coded using Medical Dictionary for Regulatory Activities (MedDRA) version 18.0 or higher.

The terms used in the CRFs by Investigators to identify adverse events.

An adverse event (AE) is defined as having a start date on or after the date of first dose through 7 days after study drug discontinuation (14 days for serious adverse events and deaths) for subjects who complete or discontinue this study but do not enter into the extension study), or through the last study day of the double-blind treatment period for subjects continuing into the extension study.

A discontinuation-emergent adverse event (DEAE) is defined as an AE with a start date after the date of last dose of study drug through the last study visit in the withdrawal period for subjects who either complete the 12-week treatment period but do not enter into the extension study, or for subjects who are terminated early in the treatment period.

The summary of overall AEs (and SAEs) will be limited to AEs and DEAEs.

The overall incidence (ie, number and percent of subjects with one or more AE in each category) of AEs, serious AEs, deaths, AEs leading to discontinuation, study drug-related AEs, serious study drug-related AEs, study drug-related AEs leading to discontinuation, and serious AEs leading to discontinuation, serious study drug-related AEs, will be summarized by treatment group.

The AEs also will be summarized by system organ class (SOC) and preferred term (PT) by presenting the number and percentage of subjects with each AE category. The incidence of AEs (by PT, grouped by SOC, and presented by treatment group) also will be summarized by severity, by the relationship to study medication, by the action taken regarding the study medication, as well as by the outcome.

The overall incidence of DEAEs and serious DEAEs will be summarized by treatment group. The DEAEs also will be summarized by SOC and PT by presenting the number and percentage of subjects with each AE category.

The incidence of AEs of special interest, including but not limited to neuropsychiatric-related and cardiovascular-related AEs, will be summarized by treatment group.

15.4.2.2. Clinical Laboratory Assessments

Treatment Period

Laboratory data will be summarized by presenting descriptive statistics of actual values and changes from baseline and shift tables. The number and percentage of subjects with markedly

abnormal post-baseline values for selected parameters will be presented. Individual subject listings of laboratory data also will be provided.

The change from baseline value at endpoint for selected laboratory parameters (eg, hemoglobin A1c, fasting glucose, fasting total cholesterol, fasting triglycerides, fasting HDL cholesterol, fasting LDL cholesterol, fasting insulin, and hs-CRP) will be evaluated using an ANCOVA model with terms for treatment and baseline binge days group, and corresponding baseline as covariate or nonparametric rank ANCOVA, when appropriate.

Withdrawal Period

Laboratory data will be summarized by presenting descriptive statistics of actual values, change from baseline, and changes from Week 12/EOT by treatment.

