7.4.3.1 Treatment Period

Descriptive statistics (N, mean, standard deviation, median, and range) will be reported for each continuous laboratory analyte at baseline, each scheduled post-baseline time point, and endpoint for observed value as well as change from baseline. Categorical results (eg, urinalysis tests) will be summarized at each visit by treatment group using frequency and percentage. If a subject has more than one measurement at any time point, the one closest to the scheduled visit will be used in the by-visit analysis. All lab values will be presented in the data listings.

Results for glucose and lipid tests (HDL cholesterol, LDL cholesterol, total cholesterol, and triglycerides) will be presented separately by fasting status, which includes fasting only and overall (fasting, non-fasting, or unknown). The change from baseline value at endpoint for these selected laboratory parameters (ie, lipid tests, glucose, HbA1c, and insulin), will be evaluated using a nonparametric rank ANCOVA. For the comparison of each dasotraline group versus placebo group, the change from baseline at endpoint and baseline value is ranked. A linear regression will be conducted on the change from baseline ranks and baseline value rank as independent variable to produce regression residuals. Using the values of the residuals as scores, Mantel-Haenszel row mean score tests will be produced for each dasotraline group versus placebo group.

In addition, the change from baseline value at Weeks 6, 12, and endpoint for these selected laboratory parameters (ie, lipid tests, glucose, HbA1c, and insulin), will be further evaluated

321

using an ANCOVA model which includes terms for treatment, baseline binge days group, and the corresponding baseline as covariate. The LS means of treatment differences (each dasotraline group minus placebo group) and 2-sided 95% CIs will be obtained from the model.

The normal reference ranges for laboratory tests will be used to determine whether the laboratory test value is below, within, or above the normal range. Shifts from baseline to endpoint will be produced by treatment group to show the percentage of subjects with laboratory test values below, within, and above the normal range.

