Criteria for Markedly Abnormal Post-baseline Laboratory Values (MAPLV) per International System of Units (SI) of selected laboratory parameters can be found in [Table 8](#). Equivalent MAPLV criteria for conventional unit are provided in [Attachment 9.5.2](#). The criterion of MAPLV is satisfied if a value falls into the markedly abnormal range at an assessed visit or if subjects have experienced at least once MAPLV in the study period. The number and percentage of subjects with a particular MAPLV at each post-baseline visit, endpoint, and during the post-baseline double-blind phase (up to and including endpoint), regardless of baseline value, will be presented by treatment group.

**Table 8 Criteria for Markedly Abnormal Post-baseline Laboratory Values (MAPLV)
(SI Unit)**

Laboratory Test	Criteria for Markedly Abnormal Status	
	Low	High
Hematology		
Hematocrit	Male: ≤ 0.37 Female: ≤ 0.32	Male: ≥ 0.60 Female: ≥ 0.54
Hemoglobin	Male: ≤ 115 g/L Female: ≤ 95 g/L	Male: ≥ 190 g/L Female: ≥ 175 g/L
RBC	$\leq 3.5 \times 10^{12}/L$	$\geq 6.4 \times 10^{12}/L$
Total WBC Count	$\leq 2.8 \times 10^9/L$	$\geq 16 \times 10^9/L$
Basophils	N/A	$\geq 10\%$ $\geq 1.6 \times 10^9/L$
Eosinophils	N/A	$\geq 10\%$ $\geq 1.6 \times 10^9/L$
Lymphocytes	N/A	$\geq 75\%$ $\geq 12.0 \times 10^9/L$
Monocytes	N/A	$\geq 15\%$ $\geq 2.4 \times 10^9/L$
Neutrophils	$\leq 15\%$ $\leq 0.42 \times 10^9/L$	$\geq 85\%$ $\geq 13.6 \times 10^9/L$
Platelet Count	$\leq 75 \times 10^9/L$	$\geq 700 \times 10^9/L$
Chemistry		
Albumin	≤ 25 g/L	N/A
ALP	N/A	$\geq 3 \times$ ULN
AST	N/A	$\geq 3 \times$ ULN

321

Laboratory Test	Criteria for Markedly Abnormal Status	
	Low	High
ALT	N/A	≥ 3 x ULN
Bicarbonate	≤ 16 mmol/L	≥ 35 mmol/L
Calcium	≤ 2.05 mmol/L	≥ 2.99 mmol/L
Chloride	≤ 90 mmol/L	≥ 118 mmol/L
Creatinine	N/A	≥ 176.8 μmol/L
Glucose (fasting)	≤ 2.22 mmol/L	≥ 9.71 mmol/L
Inorganic Phosphorus	≤ 0.5 mmol/L	≥ 1.7 mmol/L
Magnesium	≤ 0.6 mmol/L	≥ 1.15 mmol/L
Potassium	≤ 3 mmol/L	≥ 6 mmol/L
Sodium	≤ 126 mmol/L	≥ 156 mmol/L
Total Bilirubin	N/A	≥ 34.2 μmol/L
Total Protein	≤ 45 g/L	≥ 100 g/L
Uric Acid	Male: N/A Female: N/A	Male: ≥ 625 μmol/L Female: ≥ 506 μmol/L
Urea (BUN)	N/A	≥ 11 mmol/L
Lipids panel		
Total Cholesterol (fasting)	N/A	≥ 7.77 mmol/L
LDL Cholesterol (fasting)	N/A	≥ 5.18 mmol/L
HDL (fasting)	≤ 1.036 mmol/L	N/A
Triglycerides (fasting)	N/A	≥ 3.39 mmol/L
HbA1c	N/A	≥ 7.5%
Urinalysis		
Urine Blood	N/A	≥ 1+
Urine Glucose	N/A	≥ 3+
Urine Ketones	N/A	≥ 2+
Urine Protein	N/A	≥ 2+

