Note: ULN = Upper Limit of Normal; N/A = Not Applicable

A listing of subject data for those who have experienced at least once post-baseline MAPLV during the double-blind treatment period will be generated. Urine drug screen results will be presented for each parameter by visit and at endpoint. Number and percentage of positive and negative results will be displayed. Summary statistics of laboratory outputs will be generated per conventional units and International System of Units (SI), separately.

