7.4.5 Vital Signs, Weight, and BMI

7.4.5.1 Treatment Period

At each visit and endpoint, descriptive statistics (mean, SD etc.) will be provided by treatment group for

- Observed and change from baseline values of each vital sign parameter, including orthostatic changes in systolic blood pressure, diastolic blood pressure, and pulse rate;
- Observed and change, and percent change from baseline values in weight and BMI.

A similar MMRM model for the primary efficacy variable by using corresponding baseline will be applied for the following variables at the specified time points.

- Change and percent change from baseline in body weight (kg) at Weeks 1, 2, 3, 4, 6, 8, 10, and 12.
- Change and percent change from baseline in BMI at Weeks 1, 2, 3, 4, 6, 8, 10, and 12.

The number and percentage of subjects with Markedly Abnormal Post-baseline Vital Signs (MAPVS), defined in [Table 11.1](#), will be presented by visit, endpoint, or study period and by treatment group. Included are subjects having experienced at least once post-baseline MAPVS during the double-blind phase, up to and including endpoint.

Table 11.1: – Criteria for Markedly Abnormal Post-Baseline Vital Signs and Weight

Parameter (unit)	Markedly Low	Markedly High
SBP (supine, standing) (mmHg)	<90	≥180
	Value ≤ 90 and ≥ 20 decrease from baseline	Value ≥ 180 and ≥ 20 increase from baseline
DBP (supine, standing) (mmHg)	<50	≥105
	Value ≤ 50 and ≥ 15 decrease from baseline	Value ≥ 105 and ≥ 15 increase from baseline
Pulse rate (supine, standing) (bpm)	<50	≥120
	Value ≤ 50 and ≥ 15 decrease from	≥120 and increased >15 from

321

	baseline	baseline
Weight (kg)	≥ 7% decrease from baseline	≥ 7% increase from baseline
Temperature (°C)	N/A	Value ≥ 38.3°C and ≥0.8°C increase from baseline
Orthostatic Criteria		
SBP orthostatic criteria (mmHg)	≥ 20 mmHg reduction from supine to standing position	N/A
DBP orthostatic criteria (mmHg)	≥ 10 mmHg reduction from supine to standing position	N/A
Orthostatic tachycardia (bpm)	N/A	≥ 20 bpm increase from supine to standing position in pulse rate

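### The SAP counts markedly abnormal laboratory values regardless of baseline, with no baseline or treatment-emergent count, so pre-existing cases dilute the arm comparison for parameters without an entry limit

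*Protocol*

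**What the plan says.** Protocol 15.4.2.2 plans laboratory summaries by "descriptive statistics of actual values and changes from baseline and shift tables", and adds that subjects with markedly "abnormal post-baseline values for selected parameters will be presented". It does not say whether a subject who was already markedly abnormal at baseline counts.

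SAP 7.4.3.1 does say. A subject counts if a value falls in the Table 8 range at a visit, or at least once in the period. The counts are shown by visit, at endpoint and "during the post-baseline double-blind phase (up to and including endpoint), regardless of baseline value". No baseline column and no count restricted to new cases is specified.

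The same SAP section also plans change from baseline for each continuous analyte, a normal-range shift table, baseline-adjusted analyses of lipids, glucose, HbA1c and insulin, and listings.

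**The concern.** A count that ignores baseline mixes two groups: subjects who crossed the limit on treatment, and subjects who were past it before the first dose and stayed there. Randomization puts about the same number of the second group in every arm. Their presence pulls the risk ratio toward 1 and adds sampling noise to the difference.

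Elsewhere the SAP separates the two groups, or at least shows what is needed to do so:

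- **Adverse events (7.4.2):** treatment-emergent, with pre-dose events counted only if they worsen or become attributed to study drug.
- **QTc and other ECG parameters (7.4.4.1):** baseline counts are shown with post-baseline counts, and Table 9 includes increases from baseline.
- **Vital signs (Table 11.1):** some criteria pair a limit with a change, such as "Value ≥ 180 and ≥ 20 increase from baseline".
- **C-SSRS (Table 13):** emergence requires absence at baseline.

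Among these displays, the laboratory outlier table alone has neither an emergent or change criterion nor a baseline comparator. At stake is whether a reader comparing percentages by dose can see a drug-related excess of marked abnormalities.

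**Working it through.** **Which parameters are affected.** Compare the entry limits in Protocol 8.2 with the high limits in SAP Table 8.

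| Parameter | Excluded at screening | Table 8 limit |
|---|---|---|
| ALT/AST | ≥ 2 × ULN (above ULN with a hepatitis history) | ≥ 3 × ULN |
| Fasting glucose, high | ≥ 7.0 mmol/L | ≥ 9.71 mmol/L |
| HbA1c | ≥ 6.5% | ≥ 7.5% |
| HDL | none | ≤ 1.036 mmol/L |
| LDL, triglycerides | none | ≥ 5.18, ≥ 3.39 mmol/L |
| Urine blood | none | ≥ 1+ |
| Hematology | none | various |

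In the first three rows an eligible subject is below the marked limit at screening, so ignoring baseline costs almost nothing, apart from a rise between screening and Day -1. In the other rows only investigator judgment applies (exclusion 28; Protocol 12.2), while BMI up to 45 kg/m² is allowed.

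**Inputs.** The documents state no rate of marked abnormality, so there is no planned figure to reproduce. From Protocol 15.1: 160 randomized per arm, which follows from 96/(1 − 0.40) = 160. Assumed: new onset *e* of 2% on placebo and 6% on drug among subjects not abnormal at baseline; 80% of baseline abnormalities persist; baseline prevalence *b* from 1% to 30%.

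**Formulas.**

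- Displayed rate: p = 0.8b + (1 − b)e
- SE of the difference: √[p₀(1 − p₀)/160 + p₁(1 − p₁)/160]
- Emergent-only: 160(1 − b) subjects per arm, rates 2% and 6%, difference 4.0 points, risk ratio 3.0

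Example at b = 15%: placebo 0.12 + 0.85 × 0.02 = 13.7%; drug 0.12 + 0.85 × 0.06 = 17.1%; ratio 17.1/13.7 = 1.25; SE 4.03 points; 3.4/4.03 = 0.8.

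| b | Displayed, placebo vs drug | Risk ratio | Difference (points) | Difference/SE, as planned | Difference/SE, emergent-only |
|---|---|---|---|---|---|
| 1% | 2.8 vs 6.7% | 2.4 | 4.0 | 1.7 | 1.8 |
| 5% | 5.9 vs 9.7% | 1.6 | 3.8 | 1.3 | 1.8 |
| 15% | 13.7 vs 17.1% | 1.25 | 3.4 | 0.8 | 1.7 |
| 30% | 25.4 vs 28.2% | 1.1 | 2.8 | 0.6 | 1.5 |

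**Chance baseline imbalance.** Under the formula, a baseline case changes a subject's chance of being counted by 0.8 − e, that is 0.78 on placebo and 0.74 on drug. At b = 15% the contribution to the displayed difference is √[(0.15 × 0.85/160) × (0.78² + 0.74²)] = 3.0 points, against a signal of 3.4. This is already inside the SE above. The same formula gives 1.9 points at 5% and 3.9 points at 30%.

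**Second set of assumptions.** With 2% vs 8% onset and full persistence, nominal two-proportion power for the planned count against the emergent count is 61% vs 69% at 1% prevalence, 40% vs 67% at 5%, 28% vs 65% at 10% and 12% vs 54% at 30%. The pattern is the same. No such test is planned; power serves here only as a measure of visibility.

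**The case against.** The strongest reply is that this table does not stand alone.

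- **Lipids** have baseline-adjusted analyses: Protocol 15.4.2.2 provides for ANCOVA with "corresponding baseline as covariate or nonparametric rank ANCOVA, when appropriate", and SAP 7.4.3.1 plans rank ANCOVA at endpoint and ANCOVA at Weeks 6, 12 and endpoint.
- **Shift tables:** "Shifts from baseline to endpoint will be produced by treatment group to show the percentage of subjects" below, within and above the normal range.
- **Listings:** the SAP plans "A listing of subject data for those who have experienced at least once post-baseline MAPLV", and all laboratory values are listed, so baseline status can be traced subject by subject.
- **Adverse events:** clinically significant post-dose abnormalities are recorded as AEs (Protocol 12.2) and are then summarized as treatment-emergent.
- **Status:** SAP 7.4.1 declares the safety analyses descriptive.

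All of this is correct, and it means that a drug effect on laboratory values has other ways to appear. It does not supply the missing number. The ANCOVAs compare average or ranked change in a few analytes, not outliers, and do not cover hematology or urinalysis. The shift table uses normal ranges rather than Table 8 limits, and takes endpoint rather than the worst value, so a marked value at Week 6 that resolves does not appear. The listings give no rate or denominator by arm. AE recording depends on the investigator's judgment of clinical significance.

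The comparison with vital signs also needs care: Table 11.1 keeps unpaired limits, such as SBP ≥ 180 mmHg, beside the paired ones. The contrast is that a change-based criterion exists there, not that every criterion has one.

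**Conclusion.** The gap is real but narrow. For lipids, hematology and urinalysis, the planned count cannot separate pre-existing from new marked abnormalities, and no other planned display gives an emergent rate by arm. The dilution rests on assumed prevalence, persistence and onset rates. It is small at 1% prevalence and substantial from about 5% upward. The risk ratio suffers more than the risk difference.

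A reader might infer three stronger things that the documents do not support:

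- **That pre-existing abnormality swamps any drug effect.** No baseline prevalence is given, and for ALT/AST, high fasting glucose and HbA1c the entry limits sit below the Table 8 limits.
- **That chance imbalance outweighs the signal.** At 15% prevalence the imbalance in baseline prevalence itself has an SE of √(2 × 0.15 × 0.85/160) = 4.0 points, which looks larger than the 3.4-point signal. Only about 3.0 points of it reach the table. Noise exceeds signal only toward the top of the assumed range, and it is noise, not bias.
- **That the protocol prescribes the rule.** Protocol 15.4.2.2 is silent on baseline status; the rule is in the SAP.

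This is a cheap improvement to a descriptive table. It does not threaten the trial's safety conclusions as a whole.

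**What to change.** Change SAP 7.4.3.1 only; Protocol 15.4.2.2 is compatible as it stands. For each Table 8 criterion:

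1. Keep the present count regardless of baseline.
2. Show the number and percentage meeting the criterion at baseline beside it.
3. Add a treatment-emergent count. Numerator: subjects who meet the criterion after baseline but not at baseline. Denominator: subjects with a non-missing baseline that does not meet it and at least one post-baseline value.

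The baseline rule in SAP 6.1.2.2, which falls back on the latest earlier value, should leave few subjects without a baseline.

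The cost is one extra column set from data already collected, to be specified before database lock. The emergent denominator is smaller where baseline abnormality is common: 152, 136 and 112 of 160 per arm at 5%, 15% and 30% prevalence. The emergent count also leaves out subjects who were already past the limit and got worse, which is why the present count should stay.
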